22. Day 1 clinical laboratory assessments may be performed within 2 days prior to the Day 1 clinic visit. Clinical laboratory tests drawn for analysis on Day 15 of each cycle may be used for determining if the retreatment criteria have been met, and must be reviewed by the investigator or designee prior to the next cycle of study drug administration (see [Section 8.2.6](#)).
23. Intratumoral INXN-2001 [REDACTED] injection should be given 3 hours \pm 30 minutes after the INXN-1001 dose. Lesions displaying signs of local infection should not be injected. Subjects must be adequately hydrated on each day of study drug administration, and must be instructed to maintain good oral hydration on and between dosing days. Each subject will be carefully monitored for possible local reactions at the injection site and/or hypersensitivity reactions, for at least 2 hours following the INXN-2001 injection. A detailed description of physical location(s) of the injected tumor(s) and surrounding tissue, and any visible local reactions will be documented. The subject should be instructed to call the clinical site if any such reactions develop or don't resolve within 24 to 48 hours. Please refer to [Section 8.2.5](#) for additional information.
24. The first INXN-1001 dose will be given on Day 1 at the clinical site in a fed state (30 minutes after the start of a normal meal) and at least 4 hours before another meal and then the remaining 6 doses will be self-administered every other day at the same time (± 1 hour) in the fed state. Subjects must be adequately hydrated on each day of study drug administration, and must be instructed to maintain good oral hydration on and between dosing days. [REDACTED]

[REDACTED] Study sites must verify compliance with INXN-1001 dosing on Days 5, 11, and 13. Subjects should return bottles of INXN-1001 for reconciliations to determine extent of subject adherence to self-administration preferably on the Day 15 visit of each cycle. Please refer to [Section 8.2.5](#) for additional information.

25. Review and reconcile returned treatment container(s) and remaining capsules to assess the degree of adherence. All subjects will be queried about dose schedule adherence and reasons for missed doses.

26. FOR CYCLE 1 ONLY: Subjects will undergo an INXN-1001 pharmacokinetic (PK) assessment. Blood samples for INXN-1001 PK analysis should be obtained on the following days and time points:

Day 1: Pre-dose (< 30 minutes prior to INXN-1001 dosing)

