9.2 Baseline

Unless otherwise specified, baseline is the last observation before the first study drug administration.

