9.3 Missing Data

If there are partial dates which require imputation, the day and/or month and/or year will be imputed in a conservative manner i.e. for the start dates, if only the day is missing, it will be imputed with the first day of the month. If the month is also missing, it will be imputed with the 1st January. For the end dates, if only the day is missing, it will be imputed with the last day of the month and if the month is also missing, it will be imputed with the 31st December. In addition, imputed dates for data that is

expected to occur on study will be modified to be consistent with appropriate known study visit dates.

Missing values for safety measures at Baseline such as laboratory data, vital signs and electrocardiogram (ECG) data will be substituted by values from the screening visit, where available.

No further imputations for missing data will be made.

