12.3 Laboratory Evaluations

Laboratory data for blood chemistry, hematology, and urinalysis will be collected throughout the study.

The following laboratory tests are to be performed as indicated by the schedule of assessments:

| Blood Chemistry | Hematology | Urinalysis |
|----------------------------|--------------------------------|--------------------|
| Albumin | Basophils | Appearance |
| Alanine aminotransferase | | pH |
| Alkaline phosphate | Eosinophils | Specific gravity |
| Aspartate aminotransferase | Platelets | Glucose |
| Bicarbonate | Red blood cell (RBC) | Protein/Albumin |
| Total bilirubin | Hepatitis C Virus | RBC Hgb |
| Blood urea nitrogen | Hemoglobin (Hgb) | Ketones |
| Calcium | Hematocrit | Bilirubin |
| Chloride | International Normalized Ratio | Nitrates |
| Creatinine | Mean corpuscular volume | Leukocyte esterase |
| Gamma glutamyl transferase | Mean corpuscular hemoglobin | |
| Glucose | Neutrophils | |
| Lactic dehydrogenase | Partial thromboplastin time | |
| Potassium | Reticulocytes | |
| Phosphorus | White blood cell | |
| Sodium | | |
| Total protein | | |

Shift tables will be constructed for the clinical chemistry and hematology data showing the shift from the baseline value to the worst (minimum or maximum value) post baseline.

The absolute value and the change from baseline will be tabulated for each scheduled time-point during the study for all continuous urinalysis parameters. Baseline is defined as the Screening value.

Details of clinical chemistry and hematology data will be listed including converted values and showing reference ranges and flagging of abnormal findings and their clinical significance. Out of reference range values will be flagged as high (H) or low (L) in the listing. Laboratory reference ranges will be presented by site.

Pregnancy test details at Screening (serum) and Day 1 of each cycle (urine) will be listed.

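### SAP 12.3 takes Screening as the urinalysis baseline, out of line with SAP 9.2 and 9.3, and leaves room to misapply it to the chemistry and hematology shift tables

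*SAP*

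**What the plan says.** - SAP 9.2 gives the general rule: "Unless otherwise specified, baseline is the last observation before the first study drug administration".
- SAP 9.3, on missing safety measures at baseline, says that values "such as laboratory data, vital signs and electrocardiogram (ECG) data will be substituted by values from the screening visit, where available".
- SAP 12.3 first deals with two panels: "Shift tables will be constructed for the clinical chemistry and hematology data showing the shift from the baseline value to the worst" value after baseline. That paragraph has no baseline definition of its own.
- The next paragraph of SAP 12.3 plans absolute values and changes from baseline "for each scheduled time-point during the study for all continuous urinalysis parameters", and closes with "Baseline is defined as the Screening value".
- SAP 12.4 defines the vital-signs baseline as the latest value before the first INXN-1001 dose.
- Protocol Table 2 marks hematology, chemistry and urinalysis in the Day -28 to -7 screening column and again on Day 1 of every cycle. The Appendix 5 schedule for Phase I and Phase II Group 1 has the same marks. Footnote 22 adds: "Day 1 clinical laboratory assessments may be performed within 2 days prior to the Day 1 clinic visit".

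**The concern.** The SAP has a sound default, the most recent value before treatment, and departs from it for one laboratory panel without saying why. The value it picks is the older of two scheduled values. Whatever happens to a patient between Screening and first dose then appears in a table headed change from baseline, where a reader will take it as change on treatment.

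The placement adds a second risk. The sentence is short and unqualified and stands in a section that covers all three panels. A programmer could apply it to the chemistry and hematology shift tables as well. A pre-dose Cycle 1 Day 1 sample would then become a post-baseline value and could itself be the worst result, before any drug was given.

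Safety is the primary objective and SAP 9.0 plans no inferential statistics, so these tables are read at face value.

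**Working it through.** The documents give no sample-size, power or error-rate figure on this point, so there is no figure of the plan's own to reproduce. The check sets the rules side by side, works out the timing, and then illustrates size.

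**1. Do the rules agree?** Suppose a patient has a Screening urinalysis and a later one drawn before dosing.
- SAP 9.2 selects the later sample. Screening is used only if nothing later exists.
- SAP 9.3 leads to the same value: Screening replaces a missing baseline. The rule presupposes a laboratory baseline other than Screening.
- SAP 12.3 selects Screening even when the later sample exists. For any panel under this sentence, the 9.3 rule has nothing to do.
- SAP 12.2 treats adverse events starting after screening but before study drug as not treatment-emergent. A Screening baseline puts the same interval after baseline.

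**2. Timing (Protocol Table 2 and footnote 22).**
- Screening laboratory sample: 7 to 28 days before Day 1.
- Day 1 laboratory sample: 0 to 2 days before the Day 1 visit.
- Time between them: from 7 − 2 = 5 days to 28 − 0 = 28 days.

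**3. What enters the change score.** For a later visit t,

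change from Screening = (value at t − Day 1 value) + (Day 1 value − Screening value).

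The second bracket is wholly pre-treatment if the Day 1 sample precedes dosing. A Screening baseline keeps it; a last-pre-dose baseline removes it.

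**4. Illustration.** None of these assumptions comes from the documents: no drug effect; a drift of 0, 0.25 or 0.5 SD, all before dosing; within-subject correlation 0.6, 0.8 or 0.9; three post-dose visits; upper limit of normal at 1.96 SD; 200,000 simulated subjects per scenario. Ranges run over the three correlations. The shift columns give the percentage of subjects normal at baseline who shift to high. They matter only if the Screening definition were also applied to the shift tables.

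| Drift (SD) | Mean change, Screening baseline (SD) | Mean change, Day 1 baseline (SD) | Shift: Screening baseline, Day 1 counted as post-baseline | Shift: Screening baseline, Day 1 not counted | Shift: Day 1 baseline |
|---|---|---|---|---|---|
| 0 | 0.000 to 0.002 | -0.002 to 0.001 | 2.6–6.0% | 2.2–4.8% | 2.2–4.8% |
| 0.25 | 0.248 to 0.249 | -0.002 to -0.001 | 5.6–10.2% | 4.9–8.4% | 3.6–7.7% |
| 0.5 | 0.499 to 0.500 | -0.001 to 0.000 | 9.9–16.7% | 8.8–14.0% | 5.3–11.9% |

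Mean change carries the whole pre-treatment drift under a Screening baseline and essentially none under a Day 1 baseline.

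**5. In patients.** SAP 1.0 gives 3 + 3 + 3 + 4 = 13 treated in Phase I and 4 + 4 + 3 + 2 = 13 in Phase II. At 0.5 SD drift, expected false shifts per parameter among 13 patients (Screening baseline with Day 1 counted, against Day 1 baseline) are:
- correlation 0.6: 2.17 − 1.54 = 0.63
- correlation 0.8: 1.62 − 1.03 = 0.59
- correlation 0.9: 1.29 − 0.69 = 0.60

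So the excess is at most about 0.6 patient per parameter per phase. Part of it comes from counting a pre-dose sample as post-baseline: even with no drift, that raises the rate from 2.2–4.8% to 2.6–6.0%.

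**The case against.** The strongest reply concerns scope. The sentence closes a two-sentence paragraph on continuous urinalysis parameters, and 9.2 opens by allowing exceptions. Chemistry and hematology therefore stay under 9.2, where 9.3 works as written. Urinalysis is a dipstick panel in which pH and specific gravity are the evident continuous items. It has no shift table, and its results are also listed by patient (Listing 16.2.8.4). If Cycle 1 Day 1 is printed as a time point in Table 14.3.3.3, a reader can see the pre-treatment change there.

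Most of this stands. A reader might infer that SAP 12.3 sets the baseline for every laboratory test, and that with 2 to 4 patients per cohort one misassigned shift moves a cohort percentage by 1/4 to 1/2, or 25 to 50 points. The documents do not support that. The natural reading confines the sentence to urinalysis, the only shift tables are 14.3.3.1 and 14.3.3.2, and nothing shows that any shift would be misassigned. Nor does 12.3 formally contradict 9.2.

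It is also true that no section requires the Day 1 laboratory sample to precede INXN-1001. Footnotes 6 and 9 to Table 2 do so for vital signs and the urine pregnancy test. Footnote 22 makes a pre-dose sample likely, not certain.

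What the reply does not supply is a reason for the exception, a role for 9.3 in urinalysis, or wording that keeps the sentence out of the shift tables.

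**Conclusion.** The point holds for urinalysis, as a minor defect and a free improvement. SAP 12.3 prefers an older baseline to a later scheduled one without a reason and does not fit 9.3. As written, change over the 5 to 28 days before treatment is tabulated as change from baseline in Table 14.3.3.3. This assumes that the Day 1 sample was in fact drawn before dosing.

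For chemistry and hematology the risk is one of misapplication, not of a stated rule. Its size, about 0.6 patient per parameter in a phase of 13, rests on the assumed drift of 0.5 SD, the normal model and the counting of Day 1 as post-baseline. With less drift it is smaller.

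A reader might go further and infer that the trial's safety conclusions are at risk. They are not: adverse events, DLTs and dose decisions do not use this baseline, and only descriptive tables are affected.

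**What to change.** - Delete the baseline sentence in SAP 12.3.
- State that urinalysis, chemistry and hematology all follow 9.2: the latest value confirmed to precede the first study drug, with Screening as the 9.3 fallback. A Day 1 sample that cannot be confirmed as pre-dose is then not used as baseline.
- State that a pre-dose Cycle 1 Day 1 sample is not a post-baseline value in Tables 14.3.3.1 to 14.3.3.3.

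If there is a reason to keep Screening for urinalysis, the SAP should give it and limit the sentence to that panel by name. The cost is a few lines of SAP text and the matching programming. No new data are needed.

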12.4 Vital Signs

Vitals signs will be collected throughout the study as detailed below. Details of vital signs including oral temperature (°C), respiratory rate (breaths/min), heart rate (bpm) and blood pressure (systolic and diastolic) (mmHg) will be listed and the number and percentage of patients will be tabulated by scheduled timepoint.

The absolute and change from baseline in vital signs will be summarized descriptively for the SAF. Baseline is defined as the last observation before the first study dose of INXN-1001.

Vitals signs will be listed.

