8.4.2.5 Vital Signs

Vital signs will include blood pressure, pulse, temperature, and respiration. Blood pressure is to be monitored closely to prevent hypotension for up to 72 hours after administration of INXN-1001. Blood pressure assessment is required on Day 3 or Day 4 for Cycle 1 and Cycle 2. Subjects must be instructed to maintain adequate oral hydration on and in between dosing days; sites must closely monitor subjects' hydration status.

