1.0 Version Control

This Statistical Analysis Plan (SAP) is based on the protocol ATI001-101 Amendment 7, issued 29 April 2013.

The planned enrollment for this study was approximately 30 patients (3 patients per dose level cohort) in Phase I and approximately 15 patients enrolled in Phase II at a single dose level at or below the Maximum Tolerated Dose (MTD).

Enrollment proceeded as follows:

Three patients were treated in cohort 1 at 5mg QD of INXN-1001, three patients treated in cohort 2 at 20mg QD, three patients treated in cohort 3 at 100mg QD, and 4 patients were treated at 160mg QD.

Four patients were treated in the expansion cohort (Phase II) at 160mg QD and four at 160mg QOD. A decision was then taken by the SRC to enroll into the expansion cohort at a reduced dose of INXN-1001; a further three patients were treated at 120mg QOD and two patients were treated at 80mg QOD, due to dose limiting toxicities (DLTs) occurring on the 160mg QOD and the 120mg QOD dose cohorts.

Further details of subject enrollment will be presented in the Clinical Study Report (CSR). This SAP describes the changes to the planned analysis along with the modified analysis for the amended design.

This SAP refers to the final analysis of the data. Pharmacokinetic (PK) data presentations and analysis will be performed by ZIOPHARM. No further details of PK analysis will be included in this SAP, with the exception of listing eCRF data.

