6.0 Patient Disposition

6.1 Sample Size

No formal sample-size estimation was performed.

Thirteen patients were treated in Phase I and 13 patients were treated in Phase II.

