9.0 Data Reporting Conventions

All listings will be ordered by phase, group (for Phase II only) and INXN-1001 actual initial dose (5mg QD, 20mg QD, 100mg QD, 160mg QD in Phase I; 160mg QD, 160mg QOD, 120mg QOD, 80mg QOD in Phase II) and patient number. Listings will present all available data.

Unless otherwise stated, data will be summarized by phase and dose cohort based on the actual dose of INXN-1001 received on Cycle 1 Day 1. For Phase II, data will be summarized based on group; additionally for Group 2, data will be presented by dose cohort. The combined data for each phase will also be summarized as an 'Overall' column.

No inferential statistics will be performed.

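### Outside adverse-event reports, no planned table counts patients who ever had a blood-pressure fall of a stated size, and later-cycle changes are not taken from that cycle's own pre-dose reading

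*SAP*

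**What the plan says.** Protocol 8.4.2.5 states: "Blood pressure is to be monitored closely to prevent hypotension for up to 72 hours after administration of INXN-1001". Footnote 6 to the Table 2 schedule gives the same purpose. It also requires vital signs before INXN-1001 on Day 1 of each cycle, and hourly for two hours after the INXN-2001 injection. Protocol 8.2.3 adds blood-pressure checks on Days 1, 2 and 3 or 4 of Cycles 1 and 2.

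On analysis, SAP 12.4 says: "The absolute and change from baseline in vital signs will be summarized descriptively for the SAF". It defines baseline as the last observation before the first INXN-1001 dose. It also says the "number and percentage of patients will be tabulated by scheduled timepoint", without naming a finding, category or threshold to count. Table 14.3.4 is the only vital-sign table in the table list, and Listing 16.2.9 is the vital-sign listing.

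Elsewhere the SAP is more specific. Chemistry and hematology get a "shift from the baseline value to the worst (minimum or maximum value) post baseline" (SAP 12.3). The ECG section counts patients with investigator-reported clinically significant findings (SAP 12.5).

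**The concern.** Safety and tolerability is the primary objective, and Protocol 5.5 says the two Phase II regimens are there to compare tolerability at 160 mg. Protocol 5.3.1 reports two deaths from hypovolemic shock in an earlier trial of intravenous IL-12. A reader of the study report will therefore ask how many patients on each regimen had a material fall in blood pressure after dosing.

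The planned vital-sign table does not answer that. It summarises each timepoint across patients, so it never follows one patient to his or her lowest value. It also measures every cycle from one pre-study value, although a fresh pre-dose reading is scheduled in each cycle. In later cycles the tabulated change therefore combines any drift since study start with the acute effect of dosing.

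**Working it through.** **1. Denominators.** SAP 6.1 states: "Thirteen patients were treated in Phase I and 13 patients were treated in Phase II". The cohort sizes in SAP 1.0 reproduce this: Phase I 3 + 3 + 3 + 4 = 13 and Phase II 4 + 4 + 3 + 2 = 13. There is no power or alpha figure to check ("No inferential statistics will be performed"; "No formal sample-size estimation was performed").

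**2. Number of rows.** Per cycle, the schedule gives three Day 1 readings (one pre-dose, two hourly after injection), plus Day 2, Day 3 or 4, Day 7, Day 13 and Day 15: 3 + 5 = 8. Over six cycles, 8 × 6 = 48 on-treatment timepoints. This is an upper bound. Earlier Phase I subjects received 3 cycles, Day 3 or 4 visits in Cycles 3 to 6 are made only when feasible, and patients stop early.

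**3. Is depth visible?** SAP 9.1 gives n, mean, SD, minimum, median and maximum for continuous parameters.
- For n = 2 or 3, minimum, median and maximum are the data.
- For n = 4, the median fixes the sum of the two middle values and the SD fixes their spread.
- An enumeration of changes from −50 to +20 mmHg, rounded as SAP 9.1 specifies, found no two samples sharing the same statistics: 0 of 2,556 (n = 2), 0 of 62,196 (n = 3) and 0 of 82,251 (n = 4, even values only).

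So in the cohort columns the depth of each fall from study baseline can be read at each tabulated timepoint.

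**4. Number ever affected.** Let a_t be the number of patients with a fall at timepoint t, in a cohort of n. The rows do not link patients across timepoints, so the number ever affected is known only to lie between max(a_t) and min(n, Σa_t). Assume one patient falls at each of 6 timepoints, so max(a_t) = 1 and Σa_t = 6:

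| n | Number ever affected |
|---|---|
| 2 | 1 to 2 |
| 3 | 1 to 3 |
| 4 | 1 to 4 |
| 13 (phase overall) | 1 to 6 |

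One patient with repeated falls and several patients with one each give the same rows.

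**5. Later cycles.** For cycle k, change from study baseline = (post-dose − pre-dose in cycle k) + (pre-dose in cycle k − study baseline), that is, acute change plus drift. With assumed values:

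| Acute change (mmHg) | Drift (mmHg) | Tabulated change (mmHg) |
|---|---|---|
| −25 | +15 | −10 |
| −25 | 0 | −25 |
| −25 | −15 | −40 |
| 0 | −15 | −15 |

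A patient with a real 25 mmHg fall can be tabulated at −10, and one with no fall at −15. If the same patients contribute to both rows, subtracting the pre-dose row mean from the post-dose row mean gives the mean acute change. It does not give individual falls or a count.

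**The case against.** The strongest reply is that the SAP already covers most of this.

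- *Depth.* A reader might infer that the tables hide how deep a fall was, because a mean dilutes one patient's drop. The documents do not support that. If one patient in the phase column of 13 falls by 40 mmHg and the others do not change, the mean is −40/13 = −3.1, but the minimum printed beside it is −40. This part of the reply stands.
- *Counts.* A reader might also infer that no table counts affected patients at all. Protocol 10.3.2 has clinically significant vital-sign changes recorded as adverse events, and SAP 12.2 tabulates patients by preferred term and dose cohort, with separate tables for Grade 3 or greater and for drug-related events. This stands in part. Those counts rest on each investigator's judgement, miss falls not judged significant, and give no size in mmHg.
- *Unscheduled readings.* It is tempting to say these are collected but left out of the table. The documents establish neither. Close monitoring may be only a care instruction, and SAP 12.4 attaches the scheduled-timepoint wording to the patient count, not to the change-from-baseline sentence. Anything recorded should appear in Listing 16.2.9, since SAP 9.0 says listings present all available data.
- *Precedent.* One pre-treatment baseline agrees with SAP 9.2, and ECG intervals and urinalysis also get only absolute value and change. Laboratory shift tables use reference ranges, which the SAP does not give for vital signs. This is fair, so the laboratory comparison shows only that a worst-value summary is already used in this SAP. It does not show that one was owed to blood pressure.

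None of this supplies a count of patients per regimen with a fall of stated size, or the within-cycle fall after Cycle 1.

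**Conclusion.** The point holds as a gap in tabulation, not in data. Outside adverse-event reports, no planned table gives the number of patients per regimen who ever had a blood-pressure fall of a stated size. Change from the Cycle 1 baseline does not measure the acute post-dose fall in later cycles, and Cycle 2 lies within the period in which Appendix 3 says most toxicity was seen. Separately, the patient count in SAP 12.4 cannot be programmed as written.

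The size is moderate. With 26 patients, Listing 16.2.9 can be read by hand, but the report would then rest on a reader's own tally for a monitored harm under the primary objective. The ranges in the working assume that Table 14.3.4 is built by timepoint, which SAP 12.4 implies but does not state for the change summary. They also use invented blood-pressure values, since the documents give none. The stronger readings, that depth is hidden or that no affected patient is counted anywhere, are not supported.

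**What to change.** In SAP 12.4 and Table 14.3.4, or one companion table:

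1. For each regimen, summarise each patient's lowest post-dose systolic and diastolic pressure in Cycle 1, in Cycle 2 and overall, using all recorded readings.
2. Give the change from that cycle's own Day 1 pre-dose value as well as from study baseline. For the overall period, take the patient's largest within-cycle fall.
3. Give the number and percentage of patients by category of largest fall. The sponsor should define the categories in the SAP before the table is produced. State the denominator as patients with a pre-dose and at least one post-dose reading in the period.
4. Say what the existing patient count by timepoint counts, or delete it.

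The cost is SAP wording and one additional table from scheduled data already planned for collection. The table is descriptive only, and in cohorts of 2 to 4 its percentages will be coarse, so the counts should lead. No dosing or clinical rule changes.
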